**Figure 7-1 Schematic of Study Design**

ETT: Early Termination of Treatment; IVA: ivacaftor; LUM: lumacaftor; q12h: every 12 hours

- a Doses may be adjusted upward for changes in weight and age. See the rules for dose adjustments in Section 9.6 of the protocol.
- b Doses are those planned for Study 115B. Based on results from Study 115A and 115B, doses for subjects <6 years of age in Study 116 may be modified.
- c The Safety Follow-up Visit is required for 1) subjects who complete their ETT Visit <10 days after the last dose of LUM/IVA (Section 9.1.2.3 of the protocol); and 2) subjects who interrupt LUM/IVA treatment and complete their Week 96 Visit <10 days after the last dose of LUM/IVA; it is not required for subjects who continue onto commercially-available, physician-prescribed LUM/IVA within 2 weeks (± 4 days) of completing LUM/IVA treatment at the Week 96 or ETT Visit.
- d See Section 9.1.1 of the protocol for details regarding the timing of the Day 1 Visit.

## **7.2 Sample Size and Power**

No formal sample size calculations have been performed.

This is a long-term extension study that will enroll subjects rolled over from Study 115B.

Approximately 56 subjects were potentially eligible to be enrolled in this rollover study. Assuming a 10% dropout rate in Study 115B, 50 subjects are expected to enroll in this study.

## **7.3 Randomization**

This is an open-label study. No randomization is planned.

Subjects in the Treatment Cohort will be treated with LUM/IVA based on their weight and age. Subjects in the Observational Cohort will not receive LUM/IVA.

## **7.4 Blinding and Unblinding**

This is an open-label study. However, subjects and their legally appointed and authorized representative (e.g., parent or legal guardian) should not be informed of their study-related spirometry, sweat chloride, and LCI results during the study even if the subject permanently discontinued treatment.

## **8 ANALYSIS SETS**

Enrolled subjects are those who signed informed consent/assent form and had an enrollment date on the CRF.

**116 All Subjects Set** is defined as all subjects who were enrolled or exposed to any amount of study drug in the Study 116 Treatment Cohort.

### **8.1 Efficacy Sets**

**Full Analysis Set (FAS):** The FAS will include all subjects who were enrolled and exposed to any amount of study drug in Study 115B.

**116 Full Analysis Set (116 FAS):** The 116 FAS will include all subjects who were enrolled and exposed to any amount of study drug in Study 116 Treatment Cohort.

### **8.2 Safety Set**

**116 Safety Set:** The 116 Safety Set will include all subjects dosed in Study 115B who are exposed to any amount of study drug in the Study 116 Treatment Cohort.

### **8.3 Other Analysis Set**

**116 LCI Substudy Set:** The 116 LCI Substudy Set will include all subjects who signed informed consent/assent to the optional LCI Substudy and are enrolled and exposed to any amount of study drug in the Study 116 Treatment Cohort.

## 9 ANALYSIS PERIODS

### 9.1 Current Study Period

The **Current Study Period** starts from the first dose date of study drug in Study 116 to the last day in Study 116.

The **Treatment-Emergent Period for the Current Study Period** starts on or after the first dose date of study drug in Study 116 to 14 days (inclusive) after the last dose of study drug in Study 116 or up to the last day in Study 116, whichever occurs first.

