#### 3 SCHEDULE OF ASSESSMENTS

### 3.1 Treatment Cohort

Table 3-1 Study VX16-809-116: Treatment Cohort - Treatment Period and Safety Follow-up Visit

		Treatment Period					Safety Follow-up Visit c
Event/Assessment a	Day 1 d	Day 3 (± 1 Day)	Day 15 (± 3 Days)	Weeks 12, 24, 36, 48, 60, 72, 84 (± 7 Days)	Week 96 (± 7 Days)	As Soon as Possible After the Last Dose	2 Weeks (± 4 Days) After the Last Dose
Informed consent/assent	X						
Clinic visit	X		X	X	X	X	X
Telephone contact e		X					
Stature and weight f	X		X	X	X	X	X
Vital signs g	$X^{h}$		X	X	X	X	X
Pulse oximetry g	X		X	X	X	X	X
OEs i	X			Week 48 j	$X^{j,k}$	$X^{j,k}$	$X^{j,k}$
Full PE 	X			Weeks 24, 48, 72	X	X	X
Abbreviated PE	X m						

- a Assessments will be performed before LUM/IVA dosing unless noted otherwise.
- b If the ETT Visit occurs 10 days or later after the last dose of LUM/IVA, the Safety Follow-up Visit will not be required (Section 9.1.2.3). Subjects who prematurely discontinue LUM/IVA treatment for AEs should be followed until the AE is considered resolved.
- The Safety Follow-up Visit is required for 1) subjects who complete their ETT Visit <10 days after the last dose of LUM/IVA (footnote b and Section 9.1.2.3); and 2) subjects who interrupt LUM/IVA treatment and complete their Week 96 Visit <10 days after the last dose of LUM/IVA; it is not required for subjects who continue onto commercially-available, physician-prescribed LUM/IVA within 2 weeks (± 4 days) of completing LUM/IVA treatment at the Week 96 or ETT Visit.
- For subjects at sites activated by the time of their Study 115B Safety Follow-up Visit, their Study 116 Day 1 Visit will be on the same day as their Study 115B Safety Follow-up Visit, and any Study 116 Day 1 assessments that were specified to be performed at the Study 115B Safety Follow-up Visit does not coincide with the subject's Study 115B Safety Follow-up Visit, the subject will complete all Study 116 Day 1 assessments (except the OE if it was performed within the last 3 months before the visit). See Section 9.1.1 for details.
- e Telephone contacts will be made to assess the subject's status, any AEs, medications, treatments, and procedures.

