### Treatment-emergent Period for the Cumulative Study Period

The Treatment-emergent Period for the Cumulative Study Period is the period on or after the first dose of study drug in the previous study to 14 days (inclusive) after the last dose of study drug in Study 116 or up to the last day in Study 116, whichever occurs first. For subjects not enrolled in Study 116, the Treatment-emergent Period for the Cumulative Study Period will be

the period on or after the first dose of study drug in the previous study to 14 days (inclusive) after the last dose of the previous study, or last date of the previous study, whichever occurs first.

Other specific periods may be defined in the SAP and used for any targeted analysis as deemed necessary.

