### 9.2 Cumulative Study Period

The **Cumulative Study Period** starts from the first dose date of study drug in Study 115B to the last day in Study 116, regardless of

- 1) the planned 2-week Washout Period in Study 115B; and/or
- 2) the rollover gap between Study 115B and Study 116 (if any).

For subjects not enrolled in Study 116, the Cumulative Study Period will start from the first dose date of study drug in Study 115B to the last day in Study 115B.

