#### **10.5.2 Clinical Laboratory**

For the laboratory measurements, the raw values and change from parent study baseline of the continuous hematology and chemistry results will be summarized in SI units at each visit in the Current Study Period (including all measurements from Study 116) for the overall group based on the 116 Safety Set.

For hematology and chemistry, the number and percentage of subjects with abnormal low (<lower limit of normal [LLN]) value and with abnormal high (>ULN) value at each scheduled time point in the Current Study Period will be summarized for the overall group based on the 116 Safety Set.

The number and percentage of subjects meeting the defined threshold criteria during the Treatment-emergent Period of the Current Study Period will be provided based on the 116 Safety Set. The threshold criteria are provided in [Appendix F](#).

Results of urinalysis will be listed in individual subject data listings only. In addition, a listing containing individual subject hematology, chemistry, and coagulation values outside the reference ranges will be provided. This listing will include data from scheduled and unscheduled time points.

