e Telephone contacts will be made to assess the subject’s status, any AEs, medications, treatments, and procedures.  
f If subjects can stand unassisted and follow directions, stature should be measured as height; otherwise, stature will be measured as length. Stature and weight must be measured with shoes off and while wearing light clothing. BMI will be derived from this assessment. See Section 11.4.3 of the protocol for details.  
g The subject should rest for at least 5 minutes before having vital signs and pulse oximetry measured. See Section 11.6.4 of the protocol for details.  
h Vital signs will be measured predose and at 1 hour (± 15 minutes), 2 hours (± 15 minutes), and 4 hours (± 15 minutes) postdose on Day 1.  
i An OE will be conducted by a licensed ophthalmologist. Subjects with documentation of bilateral lens removal do not need the OE. See Section 11.6.6 of the protocol for details.  
j Subjects may complete the OE within ± 1 week of the scheduled visit.

- k An OE will be conducted at the Week 96 Visit (or the ETT Visit if the subject does not have a Week 96 Visit, unless the discontinuation is due to initiation of treatment with commercially-available LUM/IVA), or the Safety Follow-up Visit.
- l Symptom-directed PEs will occur at any time during the study if triggered by AEs or if deemed necessary by the investigator. See Section 11.6.4 of the protocol for details.
- m An abbreviated PE will be performed 4 hours ( $\pm$  30 minutes) postdose on Day 1. See Section 11.6.4 of the protocol for details

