**Table 13-1 Study VX16-809-116: Treatment Cohort - Treatment Period and Safety Follow-up Visit**

Event/Assessment a	Treatment Period					ETT Visit b	Safety Follow-up Visit c
	Day 1 d	Day 3 (± 1 Day)	Day 15 (± 3 Days)	Weeks 12, 24, 36, 48, 60, 72, 84 (± 7 Days)	Week 96 (± 7 Days)	As Soon as Possible After the Last Dose	2 Weeks (± 4 Days) After the Last Dose
Standard 12-lead ECGs n	X		X	Week 48	X	X	X
Serum chemistry o	X		X	Weeks 12, 24, 36, 48, 72	X	X	X
Hematology o				Weeks 12, 24, 36, 48, 72	X	X	X
Coagulation studies o				Week 48	X		
Urinalysis o	X			Week 48	X		
Qualitative microbiology cultures p	X			Weeks 24, 48, 72	X	X	
Immunoreactive trypsinogen	X			Week 48	X		X
Fecal elastase-1 q	X			Week 48	X		X
Sweat chloride r	X			Weeks 24, 48	X		X
LCI (optional) s	X			Weeks 24, 48	X		X
Spirometry t	X u		X	Weeks 24, 48	X	X	X
Other events related to outcome v	X		X	X	X	X	X
LUM/IVA dosing w	LUM/IVA q12h						
Observation 4 hours after the first dose	X						
Study drug count	X		X	X	X	X	

n A standard 12-lead ECG will be performed. The subject will be instructed to rest in the supine position for at least 5 minutes, if possible, before having an ECG performed. The

ECG will be performed before any other procedures that may affect heart rate, such as blood draws. See Section 11.6.5 of the protocol for details.

o See Section 11.6.2 of the protocol for details.

p See Section 11.4.7 of the protocol for details.

q Samples will be collected at the study center during the study visit; however, samples may be collected by the subject up to 24 hours before the study visit (e.g., at home) and brought to the study visit (Section 11.4.5 of the protocol). The sample may be collected pre- or postdose.

r The sweat chloride test will be conducted at approximately the same time as predose blood collections. At each time point, 2 samples will be collected, 1 sample from each arm (left and right). See Section 11.4.1 of the protocol for details.

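### SAP 9.1 opens the treatment-emergent period on the first Study 116 dose date rather than at dosing, so Day 1 pre-dose ECG, chemistry, vital-sign and SpO2 values count as emerging on Study 116 treatment

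*SAP*

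**What the plan says.** SAP 9.1 states that the treatment-emergent period for the Current Study Period "starts on or after the first dose date of study drug in Study 116". It ends 14 days after the last Study 116 dose or on the last study day, whichever is earlier.

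Footnote a of the schedule of assessments (Protocol Table 3-1, repeated in SAP Table 13-1) reads "Assessments will be performed before LUM/IVA dosing unless noted otherwise". ECG, serum chemistry, vital signs and pulse oximetry are all marked on Day 1. For vital signs, footnote h is explicit: "Vital signs will be measured predose and at 1 hour", with further readings at 2 and 4 hours.

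Day 1 follows what SAP 9.2 calls "the planned 2-week Washout Period in Study 115B", plus the rollover gap if there is one. Under SAP 10.1, baseline is the last value before the first Study 115B dose, so a Study 116 Day 1 pre-dose value is post-baseline.

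The period is used in SAP 10.5.2 to count children "meeting the defined threshold criteria during the Treatment-emergent Period of the Current Study Period". It also governs the ECG thresholds and worst-ECG shift (10.5.3), the vital-sign thresholds and blood-pressure percentile counts (10.5.4), and the shift to lowest oxygen saturation (10.5.5).

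The protocol (section 12.2) defines only a cumulative treatment-emergent period, which is "the period on or after the first dose of study drug in the previous study" up to 14 days after the last Study 116 dose or the last study day.

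**The concern.** A Day 1 pre-dose measurement shares a calendar date with the first Study 116 dose, so the date-based rule puts it inside the period. An abnormality already present before the child took any Study 116 drug is then tabulated as having emerged on it. The tables affected report the primary objective, which is safety.

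Two cases show the effect. Exclusion criterion 5 bars only liver-test abnormalities that meet the treatment-interruption criteria without a convincing alternative cause. A child with a single pre-dose ALT of 4 × ULN, normal bilirubin and no jaundice is not barred by that criterion, and would count in the Appendix F category above 3 × ULN on the strength of a value taken before dosing. Similarly, SAP 10.5.4 counts children with blood pressure at or above the 95th percentile once and twice, and a pre-dose reading can supply one of the two.

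**Working it through.** The plan states no figure for this point, so the check is on rules first and on counts second.

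**1. Does a Day 1 pre-dose record satisfy the start rule?** It falls on study day 1. The rule requires a date on or after the first-dose date, which is also study day 1. It qualifies.

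**2. Does another SAP rule remove it?**
- *Baseline (10.1):* no. Baseline predates Study 115B dosing.
- *Visit windows (Appendix C):* the first windows open after day 1, for example (1, 50] for vital signs and chemistry and (1, 176] for ECG. Day 1 therefore has no analysis window. The windows govern by-visit summaries, however, whereas the ever, worst and lowest tables are defined by the period.
- *Day 1 special handling (Appendix C):* this covers only post-dose vital signs and spirometry.

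Nothing excludes the record.

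**3. Which tables are affected?** Those that use the period and whose measurement is taken pre-dose on Day 1: chemistry thresholds, ECG thresholds, vital-sign thresholds, blood-pressure percentile categories, worst-ECG shift and lowest-SpO2 shift. Hematology and coagulation are not drawn on Day 1. Spirometry is done on Day 1, but SAP 10.5.7 gives it by-visit summaries only.

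**4. What share of the scheduled looks is it?** Counting from the schedule, Day 1 through Week 96, without early-termination or follow-up visits:
- ECG: Day 1, Day 15, Weeks 48 and 96 = 4, so 1/4 = 25%.
- Chemistry: Day 1, Day 15, Weeks 12, 24, 36, 48, 72 and 96 = 8, so 1/8 = 12.5%.
- SpO2: Day 1, Day 15, seven visits from Week 12 to Week 84, Week 96 = 10, so 1/10 = 10%.
- Vital-sign sets: 1 pre-dose + 3 post-dose on Day 1, then Day 15, seven visits and Week 96 = 13, so 1/13 = 7.7%.

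**5. Illustration of size.** Let p be the chance that one occasion meets a criterion, independent across the k occasions. The documents give no p, so 2%, 5% and 10% are assumptions.

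P(ever) = 1 − (1 − p)^k with the pre-dose record, and 1 − (1 − p)^(k−1) without it.

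For ECG (k = 4 against 3):
- p = 2%: 1 − 0.98^4 = 7.8%; 1 − 0.98^3 = 5.9%.
- p = 5%: 1 − 0.95^4 = 18.5%; 1 − 0.95^3 = 14.3%.
- p = 10%: 1 − 0.90^4 = 34.4%; 1 − 0.90^3 = 27.1%.

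The denominator is the plan's expected enrolment: 56 × (1 − 0.10) = 50.4, stated as 50. Extra children flagged = 50 × p × (1 − p)^(k−1):

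| Measurement | p = 2% | p = 5% | p = 10% |
|---|---|---|---|
| ECG (k = 4) | 0.9 | 2.1 | 3.6 |
| Chemistry (k = 8) | 0.9 | 1.7 | 2.4 |
| SpO2 (k = 10) | 0.8 | 1.6 | 1.9 |
| Vital signs (k = 13) | 0.8 | 1.4 | 1.4 |

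These figures assume that every one of the 50 contributes a pre-dose record dated on the first-dose date.

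**The case against.** **The protocol contrast.** A reader might infer that the SAP brought these values in by replacing the protocol's first dose with a first-dose date. The documents do not support that. The protocol's period starts at the first dose in Study 115B and runs on through the washout and any rollover gap, so it would have contained the Study 116 Day 1 pre-dose values anyway. SAP 9.2 uses the same date wording for the cumulative period. The problem comes from two things together: the SAP's move from the cumulative to the current study period, and a date-based start for the latter.

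**These are not untreated children.** Treatment Cohort children completed 24 weeks in Study 115B, and the plan itself counts values up to 14 days after the last dose as treatment-emergent. After a 2-week washout, Day 1 sits near the edge of such a tail. This is fair, and it narrows the issue to which study's treatment the value should be credited to. It does not justify crediting it to Study 116 dosing that had not begun.

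**Not every child is affected.** Where Day 1 is also the Study 115B Safety Follow-up Visit, assessments specified there need not be repeated (Protocol 9.1.1.1), and the SAP does not say whether those records enter the Study 116 data. If dosing moves to the next calendar day (Protocol 9.1.1.2), the earlier ECG and chemistry fall outside the period. The repeated pre-dose vital signs stay inside, and SpO2 may too, because Protocol 11.6.4 lists it with vital signs. These points stand. They also mean that inclusion may differ between children for administrative reasons.

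**The Safety Follow-up Visit.** Adding it to the schedule would give 5 ECGs, 9 chemistry panels and 11 SpO2 visits. That visit is conditional, and it falls 14 ± 4 = 10 to 18 days after the last dose, while the period closes at 14 days. The counts through Week 96 are the safer base.

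**Limited consequence.** The study is single-arm and descriptive, no hypothesis test depends on these counts, and individual data are listed. This limits the harm but does not make the counts correct.

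**Conclusion.** The concern holds for any Day 1 pre-dose ECG, chemistry, vital-sign or SpO2 record dated on the first Study 116 dose date. The SAP's rule places it in the period and no other rule takes it out. The direction is certain: an extra look can move a child only to a worse category in an ever, worst or lowest table.

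The size is not known. The ECG illustration of about 1 to 4 children in 50 rests on assumed rates of 2% to 10%, on independence between occasions, and on all 50 children contributing. Repeated readings in one child are likely to be correlated, which would generally shrink the increment, and full correlation would reduce it to zero. The 50 is also the expected enrolment for the whole study, so the Treatment Cohort could be smaller. For those rates, the figures are best read as upper values.

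A reader might conclude that all Day 1 safety data or all safety tables are distorted. They are not: spirometry, hematology, coagulation and every by-visit summary are untouched. The correction is still worth making, because it removes a one-directional error from primary safety counts at very little cost.

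**What to change.** Choose one of two equivalent changes before database lock:
- In SAP 9.1, start the treatment-emergent period for the Current Study Period at the date and time of the first Study 116 dose; or
- keep the date, flag Day 1 pre-dose records, and exclude them from the chemistry, ECG and vital-sign threshold tables, the blood-pressure percentile categories, the worst-ECG shift and the lowest-SpO2 shift.

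In either case, show the Day 1 pre-dose values separately under a pre-dose label. State that the same rule applies when the Day 1 record is held as the Study 115B Safety Follow-up Visit, so that handling does not depend on which database contains it. Day 1 post-dose vital signs stay in the period. Adverse events starting on Day 1 stay treatment-emergent unless clearly pre-dose.

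The cost is one sentence in the SAP and one flag in the analysis data. Some counts may become slightly smaller, and no data are lost from the listings.

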### 9.2 Cumulative Study Period

The **Cumulative Study Period** starts from the first dose date of study drug in Study 115B to the last day in Study 116, regardless of

- 1) the planned 2-week Washout Period in Study 115B; and/or
- 2) the rollover gap between Study 115B and Study 116 (if any).

For subjects not enrolled in Study 116, the Cumulative Study Period will start from the first dose date of study drug in Study 115B to the last day in Study 115B.

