#### **Observational Cohort**

Subject disposition will be listed based on all subjects enrolled in the Study 116 Observational Cohort.

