## 10 STATISTICAL ANALYSIS

### 10.1 General Considerations

For the Treatment Cohort, all individual subject data will be presented in data listings based on the 116 All Subjects Set.

For the Observational Cohort, listings will be provided only for disposition, demographics, and serious adverse events (SAEs). Listings will be provided based on all subjects enrolled in the Observational Cohort.

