### **10.3.2.6 Analysis of Pulmonary Exacerbation-related Other Secondary Pharmacodynamic Variables**

**Time-to-first pulmonary exacerbation:** Time-to-first pulmonary exacerbation, defined as days from study drug initiation in the Study 115B to first pulmonary exacerbation, will be analyzed using Kaplan-Meier (KM) method based on the FAS for the Cumulative Study Period. Cumulative incidence of pulmonary exacerbation will be summarized for the overall group. Subjects without an exacerbation will be considered censored at the end date of the Cumulative Study Period.

**Number of pulmonary exacerbations:** The number of pulmonary exacerbations starting during the Cumulative Study Period (including both on-treatment events and events after treatment discontinuation), normalized by the time spent in the Cumulative Study Period (last date in the Cumulative Study Period – first date in the Cumulative Study Period + 1), will be summarized for the overall group based on the FAS.

**Number of CF-related hospitalizations through last visit:** The number of CF-related hospitalizations occurring during the Cumulative Study Period (including both on-treatment events and events after treatment discontinuation), normalized by the time spent in the Cumulative Study Period (last date in the Cumulative Study Period – first date in the Cumulative Study Period + 1), will be summarized for the overall group based on the FAS.

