s The LCI assessment (only subjects who are ≥3 years of age at Study 115B screening who consent/assent to the optional LCI Substudy in Study 115B and Study 116) should be performed pre-bronchodilator. See Sections 11.1 and 11.4.2 of the protocol for details. The assessment will be performed in multiple replicates and before the spirometry assessment.

t Spirometry (only subjects who are ≥3 years of age at Study 115B screening) should be performed pre-bronchodilator. See Sections 11.1 and 11.6.7 of the protocol for details.

u Day 1 spirometry will be performed before LUM/IVA dosing and at 2 hours (± 30 minutes) and 4 hours (± 30 minutes) postdose.

- v Other events related to outcome include assessments relating to pulmonary exacerbations, administration of antibiotic therapy for sinopulmonary signs or symptoms, and hospitalizations (Section 11.4.4 of the protocol).
- w LUM/IVA will be administered q12h ( $\pm$  2 hours) within 30 minutes of consuming fat containing food (Section 9.6 of the protocol). On days of scheduled visits, the dose will be administered at the site after predose assessments have been completed. The last dose will be the dose administered before the Week 96 Visit. See Section 9.6 of the protocol for dose determination details.

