**Table 13-2 Study VX16-809-116: Observational Cohort**

Event/Assessment	Day 1a	Long-term Follow-up Telephone Contact Weeks 48 and 96 (± 4 weeks)	Early Termination Telephone Contactb
Informed consent/assent	X		
Clinic visit	X		
Telephone contact		X	X
Serious adverse events	Continuous from signing of ICF through Week 96 or Early Termination Telephone Contact		

ICF: informed consent form; IVA: ivacaftor; LUM: lumacaftor

- a For subjects at sites activated by the time of their applicable Study 115B visit (i.e., the Week 24 Visit or the Safety Follow-up Visit, if required), their Study 116 Day 1 Visit will be the same day as their applicable Study 115B visit, and any Study 116 Day 1 assessments that were specified to be performed at the applicable Study 115B visit do not need to be repeated. If the Study 116 Day 1 Visit does not coincide with the subject’s applicable Study 115B visit, the subject will complete all Study 116 Day 1 assessments. See Section 9.1.1 of the protocol for details.
- b Subjects who become eligible to receive commercially-available, physician-prescribed LUM/IVA, and who choose to continue onto commercially-available LUM/IVA, must have an Early Termination Telephone Contact to terminate study participation

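### Read literally, the Cumulative Study Period in SAP 9.2 counts Observational Cohort time in Study 116, when only SAEs are collected, towards the exacerbation rate and the Kaplan-Meier risk set

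*SAP*

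**What the plan says.** **Population.** SAP 10.3.2.6 analyses time to first pulmonary exacerbation, number of exacerbations and number of CF-related hospitalizations on the FAS. SAP 8.1 defines that set: "The FAS will include all subjects who were enrolled and exposed to any amount of study drug in Study 115B".

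**Period.** SAP 9.2 runs the Cumulative Study Period from first dose in 115B to the last day in Study 116. Its only exception begins "For subjects not enrolled in Study 116, the Cumulative Study Period will start from the first dose date of study drug in Study 115B" and ends the period on the last day of 115B. Protocol 12.2 (Analysis Period) has the same rule and the same exception.

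**Use of the period.** In SAP 10.3.2.6 both event counts are divided by time spent in the period. For Kaplan-Meier, "Subjects without an exacerbation will be considered censored at the end date of the Cumulative Study Period".

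**Who is enrolled.** SAP 8 says: "Enrolled subjects are those who signed informed consent/assent form and had an enrollment date on the CRF". This is not limited to one cohort, and SAP 7.1 says the study consists of both. The documents also call Observational subjects enrolled. Protocol 12.3.2.1: "Subject disposition will be listed based on all subjects enrolled in the Study 116 Observational Cohort". SAP 10.1: "Listings will be provided based on all subjects enrolled in the Observational Cohort".

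**What is collected.** The Treatment Cohort schedule (SAP Table 13-1) has a row for exacerbation data, with the footnote "Other events related to outcome include assessments relating to pulmonary exacerbations, administration of antibiotic therapy for sinopulmonary signs or symptoms, and hospitalizations". The Observational schedule (SAP Table 13-2) has no such row. It lists consent, a Day 1 clinic visit, telephone contacts and SAEs, the last "Continuous from signing of ICF through Week 96 or Early Termination Telephone Contact". Protocol 13.1.1.3 confirms that only SAEs are collected for this cohort.

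**The concern.** Under Protocol 11.4.4.1 an exacerbation requires a new or changed antibiotic plus listed signs or symptoms. In the Observational Cohort neither is scheduled for collection after Day 1. An exacerbation treated with oral antibiotics and not reported as an SAE would go unrecorded while the subject's time still counted.

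The two analyses are affected differently. Every Observational subject adds time to the rate denominator. In Kaplan-Meier only those still event-free at the end of 115B matter: they remain at risk and are carried as exacerbation-free for up to 96 weeks more. If SAE reports supply no events, the rate and cumulative incidence come out too low and time to first exacerbation too long.

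The summaries are for the overall group and do not split person-time by cohort, so the table itself would not show how much of the denominator lacks ascertainment.

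**Working it through.** **1. Does the literal rule reach these subjects?** Every route into the Observational Cohort (Protocol 8.1) requires at least 4 weeks of 115B dosing, so all are in the FAS. They are enrolled in Study 116, so the exception does not apply and their period ends on their last day in Study 116. Where the SAP means treated subjects only, it names the Study 116 Treatment Cohort (the 116 sets in SAP 8 to 8.3). SAP 9.2 does not.

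**2. The plan's own figure.** SAP 7.2: 56 potentially eligible, 10% dropout in 115B. 56 × 0.90 = 50.4, stated as 50. It reproduces.

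**3. Inputs.**
- 115B time: 24 weeks of treatment (Protocol 9.3.1) + 2 weeks of washout (SAP 9.2) = 26 weeks.
- Study 116 time: 98 weeks at most in the Treatment Cohort, 96 in the Observational Cohort (Protocol synopsis).
- Assumed: 56 subjects in the FAS; n = 0, 1, 3 or 6 Observational subjects among the 50 enrolled; the other 6 contribute 13 weeks each in 115B (taking 0 or 26 instead moves the results by about 0.1 point).

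Each Observational subject has 26 ascertained weeks and up to 96 without exacerbation ascertainment: 96/122 = 79%.

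**4. Rate.** Unascertained share of the denominator = 96n / [(50 − n) × 124 + n × 122 + 6 × 13].

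| n | Calculation | Share |
|---|---|---|
| 0 | 0 | 0% |
| 1 | 96/6276 | 1.5% |
| 3 | 288/6272 | 4.6% |
| 6 | 576/6266 | 9.2% |

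If the Observational subjects come instead from the six who stopped in 115B (Protocol 8.1 admits those who discontinued drug but stayed through Week 24), n = 6 gives 576/(50 × 124 + 6 × 122) = 576/6932 = 8.3%. If all 56 enter Study 116 with 122 weeks each, the shares are 96/6832 = 1.4%, 288/6832 = 4.2% and 576/6832 = 8.4%.

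**5. Direction.** Let p be the fraction of Observational exacerbations captured through SAE reports and counted, and r the hazard in Observational time relative to ascertained time. Relative change in the reported rate = share × (p × r − 1).
- p = 0: the rate is too low by exactly the share, whatever r is.
- p = 0.5, r = 1: too low by 0.8%, 2.3% or 4.6% for n = 1, 3, 6.
- p = 0.5, r = 2: no bias. Above p × r = 1 the sign reverses.

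**6. Shorter follow-up (p = 0; n = 1, 3, 6).**
- Both cohorts average 48 weeks in Study 116: 48/3778 = 1.3%, 144/3778 = 3.8%, 288/3778 = 7.6%.
- Only Observational subjects leave at 48 weeks: 48/6228 = 0.8%, 144/6128 = 2.4% (2.35%), 288/5978 = 4.8%.
- Only Treatment subjects average 48 weeks: up to 576/4066 = 14.2% at n = 6. This is an extreme, because Observational subjects who move to commercial drug must also leave.

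**7. Kaplan-Meier at Week 122** (26 + 96 weeks = 2.338 years; 26 weeks = 0.498 years), constant hazard h assumed, no SAE capture, the six early leavers censored without effect.
- Censored at the end of 115B: 1 − exp(−h × 2.338).
- Literal rule: [(50 − n) × that value + n × (1 − exp(−h × 0.498))]/50.

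| h per year | Censored at 115B | n = 1 | n = 3 | n = 6 |
|---|---|---|---|---|
| 0.5 | 68.9% | 68.0% | 66.1% | 63.3% |
| 0.3 | 50.4% | 49.7% | 48.2% | 46.0% |

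For h = 0.5 and n = 6: (44 × 0.689 + 6 × 0.221)/50 = 0.633. Simulating the estimator 3,000 times gives 68.9% and 63.3%.

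**8. Against sampling error.** At h = 0.5 about 55 to 59 events are expected in ascertained time, so the relative standard error of the rate is about 1/√59 to 1/√55, or 13.0% to 13.5%. The Kaplan-Meier standard error is about 7 points. Every base-case shift above is smaller.

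**The case against.** The best answer is that the intent is clear. The protocol synopsis puts these analyses under its Treatment Cohort heading, SAP 10.1 limits Observational Cohort output to listings, and every 116-specific set is confined to the Treatment Cohort. A programmer could reasonably leave Observational time out. This stands as evidence of intent, and this is a gap in wording, not a deliberately biased analysis. But none of that text changes the FAS, the end date or the censoring rule, and SAP 10.3 carries no cohort heading, unlike SAP 10.5. Excluding these subjects altogether would also discard their valid 115B data and contradict the FAS. At least three implementations remain open: count through Study 116, stop at 115B, or exclude.

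Two stronger inferences are tempting and not supported. One is that any Observational subject necessarily biases the results in the drug's favour. The documents do not say whether SAE-reported exacerbations are counted. If they are, the direction depends on capture and hazard, and subjects who stopped or were not approved for treatment could have a higher hazard. A subject whose first event fell in 115B does not affect Kaplan-Meier at all. The other is that the dilution would be invisible. Observational subjects are individually listed for disposition, demographics and SAEs, so their number can be seen; only the person-time split is missing from the summary.

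It is also fair that the cohort may be empty, in which case nothing changes.

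**Conclusion.** The point holds as a gap in SAP 9.2 (and Protocol 12.2) that matters if the rule is implemented literally. Unless SAE reports supply the events, the exacerbation rate and cumulative incidence are understated. For an assumed 0, 1, 3 or 6 Observational subjects with full follow-up and no SAE capture, the rate is about 0%, 1.5%, 4-5% or 8-9% too low. With 6 subjects and an assumed hazard of 0.5 per year, Kaplan-Meier incidence at Week 122 is about 63% instead of 69%. Cohort size, hazards and capture fraction are assumptions; the documents give none of them.

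For CF-related hospitalizations the direction is uncertain: admissions for an adverse event are SAEs and would be collected, but the SAP does not say that SAE records feed the count, and planned admissions may be missed.

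Priority is low to moderate. The endpoints are descriptive and secondary, SAP 10.1 plans no hypothesis testing, and the primary safety analysis uses the 116 Safety Set over the Current Study Period and is unaffected. The shift is nevertheless systematic, and cheap to prevent.

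**What to change.** - **SAP 9.2:** state that, for the pulmonary exacerbation endpoints, the Cumulative Study Period of every subject not enrolled in the Study 116 Treatment Cohort, including the Observational Cohort, ends on the last day in Study 115B.
- **SAP 10.3.2.6:** use that date for both censoring and person-time, and report how many subjects it affects.
- **CF-related hospitalizations:** apply the same end date, so that events and person-time match.

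The cost is a few sentences and one changed date derivation, with no new data. If the database is already locked, SAP 4 provides for documenting the change in the clinical study report.

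There is a trade-off to state in the report. SAP 10.3.2.6 wants events after treatment discontinuation included, and this change gives up Study 116 follow-up for Observational subjects. Their SAE-reported events in that time would appear only in the SAE listing. Censoring at the end of 115B may also be informative, because these subjects stopped, declined or were not approved for further treatment.
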